##### **4.6.2.1 Permitted, Restricted, and Prohibited Medications**

Prohibitions and restrictions for concomitant medications should be followed between the initial Baseline visit and Visit 9/ET as specified in [Appendix A](#) and [Appendix B](#). These appendices do not constitute an exhaustive list and any questions regarding prohibited and restricted medications should be discussed with the Medical Monitor or designee.

Use of medications that could interfere with study conduct or any questions regarding prohibited and restricted concomitant medications should be reviewed and/or discussed with the Medical Monitor or designee.

Medications that can prolong QT interval are prohibited (or restricted if approved by the Medical Monitor) as specified in Appendix A.

Permitted concomitant medications should remain at a stable dose throughout the study.

If a subject is on a medication restricted by the protocol, the medication should be adjusted if it is determined by the Investigator to be clinically appropriate (e.g., if the subject's

symptoms are not well-controlled or if the subject cannot tolerate the current medication) in consultation with the treating physician.

Subjects who require current treatment with a prohibited medication will be withdrawn from the study.

Subjects who have previously taken a prohibited medication during the study will be withdrawn from the study unless:

- the prohibited medication has been discontinued AND
- withdrawal from the study presents an unacceptable medical risk to the subject

The justification to allow the subject who has taken a prohibited medication to continue in the trial will be made by the Sponsor/Medical Monitor, with medical input from the Investigator, and will be documented. If a subject is allowed to remain in the trial, this will be reported as a major protocol deviation and not a waiver.

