### **6.3.4 Electrocardiograms**

All 12-lead electrocardiograms (ECGs) will be complete, standardized recordings. A single 12-lead ECG will be completed at all scheduled visits at the investigator site during the present study (Table S-1). In the US and UK, a 6-lead ECG device will be given to subjects in order to perform ECGs on themselves at home when they cannot go the clinic and site staff cannot go to their home. This should be done in discussion with the Medical Monitor. When an ECG is performed outside of the investigator site, this should be documented in the source record. All ECGs will be centrally read; the interpretation by the central cardiologist is considered the official result. If a site performs additional ECGs beyond the single ECG prescribed at Baseline, the mean QTcF/QRS values of all the tracings of adequate quality will be used to determine eligibility.

At Baseline, a subject may be enrolled based on the machine read of the locally completed ECG. If the interpretation of the ECG by the central cardiologist returned after enrollment indicates QTcF outside of the allowable range, the subject will be discontinued from the study, but this will not be considered a protocol deviation.

Electrocardiograms should be performed before blood sampling or at least 30 minutes after blood sampling. The subject must rest in a supine position for 5 minutes before the ECG is obtained. ECG tracings (paper or electronic) will be reviewed and interpreted by a qualified clinician. ECG tracings and results (ventricular rate, PR, QRS, QT, QTcF and QTcB intervals) will be included and summarized in the subject's study records.

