	
 
• bretylium
 
• disopyramide
 
• dofetilide
 
• dronedarone
 
• flecainide
 
• ibutilide
 
• procainamide
 
• propafenone
 
• quinidine
 
• sotalol, d-sotalol
 
	
Opioids	
PROHIBITED
 
 
• methadone
 
• hydrocodone
 
• oxycodone
 
• codeine
 
• morphine
 
	
 
• Prohibited at study entry and throughout the study
 
• Subjects who require chronic treatment with opioid medication or who have a substance use disorder are not eligible for this study
 
• Limited short term use of opioids for a few days only is allowed during the study for treatment of acute pain following trauma or surgical procedure
 
• Opioids should not be used within 12 hours of an efficacy assessment
 

Antimicrobials, antifungals, and antimalarials	
PROHIBITED
 
 
• clarithromycin
 
• erythromycin
 
• levofloxacin
 
• moxifloxacin
 
• pentamidine
 
• roxithromycin
 
	
 
• Prohibited at study entry and throughout the study
 

	
RESTRICTED
 
 
• arteminol/piperazine
 
• azithromycin
 
• bedaquiline
 
• ciprofloxacin
 
• gemifloxacin
 
• norfloxacin
 
• ofloxacin
 
• fluconazole
 
• telavancin
 
• telithromycin
 
	
 
• Prohibited at Baseline but may be used during the course of the study to treat a bacterial infection (e.g., urinary tract infection, respiratory infection), post-Baseline at the discretion of the Principal Investigator.
 
• The medications on the left are only allowed under the following conditions:                         
 
○ The subject has a Baseline ECG with a QTcF <425 ms IF QRS duration is <120 ms OR
 
○ The subject has a QTcF <450 ms at Baseline IF QRS duration ≥120 ms
 
 
 

a Medications within each class include but are not limited to the examples listed in this table.

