## Appendix B Prohibited and Restricted Concomitant Medications: Inhibitors and Inducers of Cytochrome P450 Enzyme 3A4

The information presented here is intended to provide guidance and does not constitute an exhaustive list of strong CYP 3A4 enzyme (CYP3A4) inhibitors and inducers. Any questions should be discussed with the Medical Monitor or appropriate designee.

Subjects who require current treatment with a prohibited medication will be withdrawn from the study.

Subjects who have previously taken a prohibited medication during the study will be withdrawn from the study unless:

- the prohibited medication has been discontinued AND
- withdrawal from the study presents an unacceptable medical risk to the subject

The justification to allow the subject to continue in the study will be made by the Sponsor/Medical Monitor with medical input from the Investigator, and will be documented. If allowed to remain in the study, this will be reported as a major protocol deviation and not a waiver.

The metabolism of pimavanserin is affected by strong CYP3A4 inhibitors, resulting in an increase in maximum (peak) observed drug concentration ( $C_{max}$ ) of approximately 1.5-fold and area under the plasma concentration-time curve (AUC) of approximately 3-fold.

Strong inhibitors of CYP3A4 are to be stopped at least 7 days or 5 half-lives prior to investigational product administration, whichever is longer. Strong inducers of CYP3A4 are to be stopped 30 days or 5 half-lives prior to investigational product administration, whichever is longer. Moderate inhibitors and inducers of CYP3A4 are allowed but should be used with caution.

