
STRONG INHIBITORS
	
grapefruit juicea                      boceprevir (Victrelis®)                      clarithromycin (Biaxin®)                      cobicistat (part of Stribild®)                      conivaptan (Vaprisol®)                      fluvoxamine (Luvox®)                      indinavir (Crixivan®)                      itraconazole (Sporanox®)                      ketoconazole (Nizoral®)                      lopinavir and ritonavir (Kaletra®)                      mibefradil (Posicor®)                      nefazodone (Serzone®)                      nelfinavir (Viracept®)                      posaconazole (Noxafil®)
	
MODERATE INHIBITORS
	
grapefruit juicea                      amprenavir (Agenerase®)                      aprepitant (Emend®)                      atazanavir (Reyataz®)                      ciprofloxacin (Cipro®)                      darunavir/ritonavir (Prezista®/Ritonavir)                      diltiazem                      erythromycin (Erythrocin® Lactobionate)                      fluconazole (Diflucan®)                      fosamprenavir (Lexiva®)                      imatinib (Gleevec®)                      verapamil (Calan®)

---------------------------------	--	-----------------------------------	--

	quinupristin (Synercid®) ritonavir (Norvir®, part of Viekira Pak™) saquinavir (Invirase®) telaprevir (Incivek®) telithromycin (Ketek®) voriconazole (Vfend®)		
STRONG INDUCERS	avasimibe carbamazepine (Tegretol®) phenobarbital (Luminal®, Solfoton®) phenytoin (Dilantin®) rifampin (Rifadin®, Rifadin® IV, Rimactane®) St. John's Wort	MODERATE INDUCERS	bosentan (Tracleer®) efavirenz (Sustiva®) etravirine (Intelence®) modafinil (Provigil®) nafcillin (Unipen®, Nallpen®)

a The effect of grapefruit juice varies widely among brands and is concentration-, dose-, and preparation-dependent. Studies have shown that it can be classified as a “strong CYP3A inhibitor” when a certain preparation was used (e.g., high dose, double strength) or as a “moderate CYP3A inhibitor” when another preparation was used (e.g., low dose, single strength). (FDA Drug Development and Drug Interactions  

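### Telithromycin may be used on treatment under Protocol Appendix A but is a strong CYP3A4 inhibitor under Appendix B; a lesser point is that the opioid row's PROHIBITED heading conflicts with the short-term use it allows

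*Protocol*

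**What the plan says.** **Telithromycin, Appendix A.** It is the last of ten drugs in the RESTRICTED antimicrobial list. The rule for that list is: "Prohibited at Baseline but may be used during the course of the study to treat a bacterial infection". Use is left to the Principal Investigator and requires a Baseline QTcF below 425 ms (QRS under 120 ms) or below 450 ms (QRS 120 ms or more). The row sets no CYP3A4 condition.

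**Telithromycin, Appendix B.** The strong-inhibitor cell ends with "telithromycin (Ketek®) voriconazole (Vfend". Strong inhibitors are said to raise pimavanserin Cmax about 1.5-fold and AUC about 3-fold. Two rules follow: "Strong inhibitors of CYP3A4 are to be stopped at least 7 days or 5 half-lives prior to investigational product administration, whichever is longer" and "Moderate inhibitors and inducers of CYP3A4 are allowed but should be used with caution". The appendix also says of itself: "The information presented here is intended to provide guidance and does not constitute an exhaustive list".

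**Section 4.6.2.1.** Both appendices apply: "Prohibitions and restrictions for concomitant medications should be followed between the initial Baseline visit and Visit 9/ET as specified in" Appendices A and B. The section adds: "Medications that can prolong QT interval are prohibited (or restricted if approved by the Medical Monitor) as specified in Appendix A".

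**Opioids, Appendix A.** The row is headed PROHIBITED, and its first bullet bars opioids at entry and for the whole study. A later bullet permits a few days of treatment for acute pain after an injury or operation, and the next keeps opioids at least 12 hours away from efficacy assessments. The introduction to Appendix A defines a prohibited drug as one that is not allowed, and a restricted drug as one allowed on conditions. Sections 4.6.2.1 and 6.3.7 require withdrawal after a prohibited drug or an opiate-positive central urine screen. The exception is a subject who has stopped the drug and for whom withdrawal would be an unacceptable medical risk; keeping that subject is a major deviation.

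**The concern.** For telithromycin the two appendices give a site opposite answers to the same question. Appendix A grants an express permission during treatment, gated only on an ECG taken at Baseline, before the interacting drug is started. Appendix B places the drug in the group with the largest stated effect on pimavanserin exposure. Protocol Section 1.3 says that pimavanserin prolongs the QT interval, and the Appendix A row itself treats QTcF as the relevant risk. What is at stake is the safety of a subject given the drug by a site that consulted only the Appendix A row.

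For opioids what is at stake is smaller. A subject who uses them as the row permits has, read literally, taken a prohibited drug, and the withdrawal and major-deviation rules contain no exception for that use. Sites could handle such subjects differently.

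**Working it through.** There is no planned figure to reproduce and no error rate or sample size is involved. The check is a comparison of the two appendices.

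**Step 1. Drugs named in both lists.**

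| Drug | Appendix B class | Appendix A status |
|---|---|---|
| clarithromycin | strong inhibitor | PROHIBITED |
| fluvoxamine | strong inhibitor | PROHIBITED |
| nefazodone | strong inhibitor | PROHIBITED |
| **telithromycin** | **strong inhibitor** | **RESTRICTED** |
| carbamazepine | strong inducer | PROHIBITED |
| phenytoin | strong inducer | PROHIBITED |
| erythromycin | moderate inhibitor | PROHIBITED |
| ciprofloxacin | moderate inhibitor | RESTRICTED |
| fluconazole | moderate inhibitor | RESTRICTED |
| modafinil | moderate inducer | PROHIBITED |

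- Strong: 4 inhibitors + 2 inducers = 6, of which 5 are PROHIBITED and 1 is RESTRICTED.
- Moderate: 3 inhibitors + 1 inducer = 4, of which 2 are PROHIBITED and 2 are RESTRICTED.
- Total: 6 + 4 = 10.
- Of the 10 restricted antimicrobials, 3 appear in Appendix B, and 1 of those 3 is strong.

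**Step 2. Which entries conflict.** Ciprofloxacin and fluconazole are consistent, because Appendix B allows moderate agents with caution and Appendix A adds conditions. Erythromycin and modafinil are barred by Appendix A and tolerated by Appendix B, so following the stricter list settles them. Telithromycin is the only drug that Appendix A expressly permits on treatment while Appendix B puts it in the strong group.

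**Step 3. Does Appendix B bar strong inhibitors on treatment?** Not in so many words. The bar follows from four features read together: the appendix title covers prohibited and restricted drugs; it repeats the withdrawal rule for prohibited drugs; strong inhibitors must be stopped before dosing; and only moderate agents are then allowed. A washout before the first dose would serve little purpose if the drug could be restarted the next day.

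**Step 4. Opioid row against the definitions.** Use that is allowed for a stated purpose, for a few days, and with a 12-hour rule fits the protocol's definition of restricted, not prohibited. The antihistamine row is built in a similar way (barred at Baseline, a few days' use for stated purposes, a 12-hour rule) and is headed RESTRICTED.

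**The case against.** The strongest answer is that the rules are cumulative. Section 4.6.2.1 makes both appendices apply, so the QTcF limits in Appendix A are conditions on use and do not waive Appendix B. A careful site would follow the stricter rule. There are other controls as well: subjects are told to consult the Investigator before taking any medicine, emergencies aside (Section 4.6.2); QT-prolonging drugs fall under Medical Monitor approval; and both Section 4.6.2.1 and Appendix B send questions to the Medical Monitor. All of this stands and lowers the risk. It does not remove the risk, because Appendix A gives an express permission at site discretion, Appendix B never states the on-treatment bar, and a site reading only the Appendix A row may see no question to raise.

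A reader might infer from the ECG schedule that the hazard can be quantified. Section 6.3.4 says "A single 12-lead ECG will be completed at all scheduled visits at the investigator site during the present study", and after Week 16 those visits fall at Weeks 28, 40 and 52, which is 12 weeks apart. That spacing applies equally to every restricted antimicrobial, and Section 6.5 lets the Investigator add any safety evaluation at an unscheduled visit. It describes the visit schedule and does not measure this defect.

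On opioids, the defence is that a general rule and its written exception sit in the same cell, and that the 12-hour rule presupposes a subject who stays in the study. Section 6.3.7 also points back to the Appendix A restrictions. Scheduled drug screens fall only at Baseline, Week 12 and Week 52 or early termination, so for a continuing subject the screen matters mainly at Week 12. This mostly stands. The intent is reasonably clear, and what is left is a heading and a withdrawal rule that do not match it.

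**Conclusion.** The telithromycin conflict is real and is a safety-relevant list error: one of six shared strong agents carries the wrong status. The conclusion rests on reading Appendix B as barring strong agents on treatment, which is implied and not stated, and on the drugs that the two lists name, neither list being exhaustive. The opioid point is secondary and minor.

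The documents do not support stronger readings:

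- **Harm or use.** Nothing shows that any subject received telithromycin. The number affected by either point is unknown.
- **A dose or QT equivalent.** The 3-fold AUC cannot be turned into an equivalent dose or a number of milliseconds, because dose proportionality is not stated and no exposure–QT relation is given.
- **Distorted deviation counts.** A reader might infer that major-deviation totals (SAP Section 7) are wrong. Classification is set in the Protocol Deviation Management Plan, which is not among the documents and may already cover permitted opioid use.
- **An effect on the results.** The primary TEAE analysis is unchanged.

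**What to change.** **Telithromycin.** Move it to the PROHIBITED antimicrobials in Appendix A, beside clarithromycin. State in Appendix B that strong CYP3A4 inhibitors and inducers are prohibited throughout treatment, and that where a drug is named in both appendices the stricter one governs.

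**Opioids.** Relabel the row RESTRICTED. Change its first bullet to bar any use at Baseline and chronic use throughout; relabelling alone would leave that bullet contradicting the allowance. Keep the QT-drug rule of Section 4.6.2.1 in force for every listed opioid, methadone included. Add to Sections 4.6.2.1 and 6.3.7 that documented short-term use permitted by Appendix A does not by itself lead to withdrawal or a major deviation.

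**Cost and timing.** The cost is low: a few lines in two appendices and two sections, with no change to the planned analyses. SAP Section 3.6 records that the study was stopped early and the remaining subjects discontinued, so the changes are for any protocol that reuses this list. Deviations in this study should not be reclassified after the fact.

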## Appendix B Prohibited and Restricted Concomitant Medications: Inhibitors and Inducers of Cytochrome P450 Enzyme 3A4

The information presented here is intended to provide guidance and does not constitute an exhaustive list of strong CYP 3A4 enzyme (CYP3A4) inhibitors and inducers. Any questions should be discussed with the Medical Monitor or appropriate designee.

Subjects who require current treatment with a prohibited medication will be withdrawn from the study.

Subjects who have previously taken a prohibited medication during the study will be withdrawn from the study unless:

- the prohibited medication has been discontinued AND
- withdrawal from the study presents an unacceptable medical risk to the subject

The justification to allow the subject to continue in the study will be made by the Sponsor/Medical Monitor with medical input from the Investigator, and will be documented. If allowed to remain in the study, this will be reported as a major protocol deviation and not a waiver.

The metabolism of pimavanserin is affected by strong CYP3A4 inhibitors, resulting in an increase in maximum (peak) observed drug concentration ( $C_{max}$ ) of approximately 1.5-fold and area under the plasma concentration-time curve (AUC) of approximately 3-fold.

Strong inhibitors of CYP3A4 are to be stopped at least 7 days or 5 half-lives prior to investigational product administration, whichever is longer. Strong inducers of CYP3A4 are to be stopped 30 days or 5 half-lives prior to investigational product administration, whichever is longer. Moderate inhibitors and inducers of CYP3A4 are allowed but should be used with caution.


STRONG INHIBITORS
	
grapefruit juicea                      boceprevir (Victrelis®)                      clarithromycin (Biaxin®)                      cobicistat (part of Stribild®)                      conivaptan (Vaprisol®)                      fluvoxamine (Luvox®)                      indinavir (Crixivan®)                      itraconazole (Sporanox®)                      ketoconazole (Nizoral®)                      lopinavir and ritonavir (Kaletra®)                      mibefradil (Posicor®)                      nefazodone (Serzone®)                      nelfinavir (Viracept®)                      posaconazole (Noxafil®)
	
MODERATE INHIBITORS
	
grapefruit juicea                      amprenavir (Agenerase®)                      aprepitant (Emend®)                      atazanavir (Reyataz®)                      ciprofloxacin (Cipro®)                      darunavir/ritonavir (Prezista®/Ritonavir)                      diltiazem                      erythromycin (Erythrocin® Lactobionate)                      fluconazole (Diflucan®)                      fosamprenavir (Lexiva®)                      imatinib (Gleevec®)                      verapamil (Calan®)

---------------------------------	--	-----------------------------------	--

	quinupristin (Synercid®) ritonavir (Norvir®, part of Viekira Pak™) saquinavir (Invirase®) telaprevir (Incivek®) telithromycin (Ketek®) voriconazole (Vfend®)		
STRONG INDUCERS	avasimibe carbamazepine (Tegretol®) phenobarbital (Luminal®, Solfoton®) phenytoin (Dilantin®) rifampin (Rifadin®, Rifadin® IV, Rimactane®) St. John's Wort	MODERATE INDUCERS	bosentan (Tracleer®) efavirenz (Sustiva®) etravirine (Intelence®) modafinil (Provigil®) nafcillin (Unipen®, Nallpen®)

a The effect of grapefruit juice varies widely among brands and is concentration-, dose-, and preparation-dependent. Studies have shown that it can be classified as a “strong CYP3A inhibitor” when a certain preparation was used (e.g., high dose, double strength) or as a “moderate CYP3A inhibitor” when another preparation was used (e.g., low dose, single strength). (FDA Drug Development and Drug Interactions  

ESRS-A	Extrapyramidal Symptom Rating Scale–Abbreviated
ET	Early Termination
GSD	Guidance for Site Documentation and Data Management Querying of Data Impacted by COVID-19
HAMD-17	Hamilton Depression Scale (17 items)
MedDRA	Medical Dictionary for Regulatory Activities
msec	milliseconds
OL	open-label
PCI	potentially clinically important
QTcB	QT interval corrected for heart rate using Bazett’s formula
QTcF	QT interval corrected for heart rate using Fridericia’s formula
SAE	serious adverse event
SAP	statistical analysis plan
SAS [®]	Statistical Analysis System
SD	standard deviation
SE	standard error
SOC	system organ class
TEAE	treatment-emergent adverse event
TESAE	treatment-emergent serious adverse event

1 INTRODUCTION

This statistical analysis plan (SAP) provides a technical and detailed elaboration of the statistical analyses of safety and efficacy data as described in the study protocol Amendment 4 dated 11 August 2020. Specifications for tables, figures, and listings are contained in a separate document.

2 OBJECTIVES

2.1 Primary Objective

- To assess the safety and tolerability of long-term pimavanserin treatment in subjects with major depressive disorder and inadequate response to antidepressant treatment

2.2 Exploratory Objectives

- To explore the safety and tolerability of long-term pimavanserin treatment in subjects with major depressive disorder and inadequate response to antidepressant treatment on the following:
 - suicidality
 - extrapyramidal symptoms
 - general health assessments
- To explore the benefits of long-term pimavanserin treatment in subjects with major depressive disorder and inadequate response to antidepressant treatment on the following:
 - improvement of depression symptoms
 - clinical global impression of severity of depressive symptoms
 - functional impairment
 - sexual functioning

